## 9 STUDY CALENDARS

Baseline evaluations are to be conducted within 2-week prior to start of protocol therapy. Scans must be done  $\leq 4$  weeks prior to the start of therapy. In the event that the participant's condition is deteriorating, laboratory evaluations should be repeated within 48 hours prior to initiation of the next cycle of therapy

All assessments must be performed prior to administration of any study medication. All study assessments and medications should be administered within  $\pm 3$  days of the protocol-specified date, unless otherwise noted.

CONFIDENTIAL

This document is confidential. Do not disclose or use except as authorized.

**Phase I Portion – Dose levels -1G, -1, 1, 1G, and 2**

	Pre-Study	C1 d1	C1 d8	C1 d9-14	C1 d15	C1 d22	C2 d1	C2 d8	C2 d15	C2 d22	C3 d1 a	C3 d8 a	C3 d15 a	C3 d22 a	Off Study c
SGI-110 Days 1-5		X					X				X				
Irinotecan			X		X			X	X			X	X		
Growth Factor Support				X f											
Informed consent	X														
History	X														
Concurrent meds	X	X	X		X	X	X	X	X		X	X	X		X
Physical exam (Ht, Wt, BSA, VS) e	X	X					X				X				X
Performance Status	X	X					X				X				X
CBC w/diff, plts	X	X	X		X	X	X	X	X		X	X	X		X
Serum chemistry b	X	X	X		X	X	X	X	X		X	X	X		X
CEA	X	X					X				X				X
Urinalysis	X	X					X				X				X
ECG	X														
Adverse event evaluation		X-----X													X
Tumor measurements	X		Repeated every 8 weeks. Documentation (radiologic) must be provided for subjects removed from study for progressive disease.												X c
Radiologic evaluation	X		Radiologic measurements should be performed every 8 weeks												X c
B-HCG	X d														
Tumor biopsy	X		X												
Archival Tissue	X														
Research Bloods		X	X		X	X	X	X	X		X				X
PK Study		X													

a: All study calendar evaluations for cycle 3 are representative of cycle 3 and beyond.                      b: Albumin, alkaline phosphatase, total bilirubin, BUN, calcium, chloride, glucose, phosphorus, potassium, total protein, SGOT [AST], SGPT [ALT], sodium.                      c: Off-study evaluation should be performed within 30 days of last dose.                      d: Serum pregnancy test (women of childbearing potential).                      e: Baseline height will be measured and recorded once during pre-study, and this value for height will be used through the patient's duration of study.                      f: Growth factor support will be initiated with filgrastim 5mcg/kg/day on cycle 1 day 9-14 for patients enrolled on Dose levels -1G and 1G. Additional growth factor support during Cycle 1 and on subsequent cycles will be provided per clinician judgment.
															

CONFIDENTIAL

This document is confidential. Do not disclose or use except as authorized.

**Phase I Portion – Dose level 3**

	Pre-Study	C1 d1	C1 d8	C1 d9-14	C1 d15	C1 d22	C2 d1	C2 d8	C2 d15	C2 d22	C3 d1 a	C3 d8 a	C3 d15 a	C3 d22 a	Off Study c
SGL-110 Days 1-5		X					X				X				
Irinotecan		X	X		X		X	X	X		X	X	X		
Informed consent	X														
History	X														
Concurrent meds	X	X	X		X	X	X	X	X		X	X	X		X
Physical exam (Ht, Wt, BSA, VS) e	X	X					X				X				X
Performance Status	X	X					X				X				X
CBC w/diff, plts	X	X	X		X	X	X	X	X		X	X	X		X
Serum chemistry b	X	X	X		X	X	X	X	X		X	X	X		X
CEA	X	X					X				X				X
Urinalysis	X	X					X				X				X
ECG	X														
Adverse event evaluation		X-----X													X
Tumor measurements	X		Repeated every 8 weeks. Documentation (radiologic) must be provided for subjects removed from study for progressive disease.												X c
Radiologic evaluation	X		Radiologic measurements should be performed every 8 weeks												X c
B-HCG	X d														
Tumor biopsy	X		X												
Archival Tissue	X														
Research Bloods		X	X		X	X	X	X	X		X				X
PK Study		X													

a: All study calendar evaluations for cycle 3 are representative of cycle 3 and beyond.                      b: Albumin, alkaline phosphatase, total bilirubin, BUN, calcium, chloride, glucose, phosphorus, potassium, total protein, SGOT [AST], SGPT [ALT], sodium.                      c: Off-study evaluation should be performed within 30 days of last dose.                      d: Serum pregnancy test (women of childbearing potential).                      e: Baseline height will be measured and recorded once pre-study, and this value for height will be used through the patient's duration of study.
															

CONFIDENTIAL

This document is confidential. Do not disclose or use except as authorized.

**Phase II Portion**  
**Arm A – SGI-110 + Irinotecan**

	Pre-Study	C1 d1	C1 d8	C1 d9-14	C1 d15	C1 d22	C2 d1	C2 d8	C2 d15	C2 d22	C3 d1 b	C3 d8 b	C3 d15 b	C3 d22 b	Off Study e
SGI-110 Days 1-5 a		X					X				X				
Irinotecan a			X		X			X	X			X	X		
Growth factor support				X--- a											
Informed consent	X														
History	X														
QoL questionnaire		X									X i				X
Concurrent meds	X	X	X		X	X	X	X	X		X	X	X		X
Physical exam (Ht, Wt, BSA, VS) g	X	X					X				X				X
Performance Status	X	X					X				X				X
CBC w/diff, plts	X	X	X		X	X	X	X	X		X	X	X		X
Serum chemistry d	X	X	X		X	X	X	X	X		X	X	X		X
CEA	X	X					X				X				X
Urinalysis	X	X					X				X				X
ECG	X														
Adverse event evaluation			X-----X												X
Tumor measurements	X		Repeated every 8 weeks. Documentation (radiologic) must be provided for subjects removed from study for progressive disease.												X e
Radiologic evaluation	X		Radiologic measurements should be performed every 8 weeks												X e
Archival Tissue	X														
B-HCG	X f														
Tumor Biopsy	X h							X h -----X h							
Research Bloods		X	X		X	X	X	X	X		X		X		X

CONFIDENTIAL

This document is confidential. Do not disclose or use except as authorized.

	
a: Arm A -Dose Level 1G from Phase I, SGI-110 45mg/m2 D1-5, Irinotecan 125mg/m2 D8 and 15. Treatment cycle is 28 days. Growth factor support of filgrastim (or institutional equivalent) 5mcg/kg/day on days 9-14 and peg-filgrastim 6mg on day 16 of cycle 1 is mandatory. Additional growth factor support during Cycle 1 and on subsequent cycles will be provided per clinician judgment.
 
b: All study calendar evaluations for cycle 3 are representative of cycle 3 and beyond.
 
c: Off-study evaluation should be performed within 30 days of last dose.
 
d: Albumin, alkaline phosphatase, total bilirubin, BUN, calcium, chloride, glucose, phosphorus, potassium, total protein, SGOT [AST], SGPT [ALT], sodium.
 
f: Serum pregnancy test (women of childbearing potential). g: Baseline height will be measured and recorded once pre-study, and this value for height will be used through the patient's duration of study
 
h: SKCCC, VUMC, MSKCCC, and USC-Norris, will obtain biopsies on a total of 36 patients (distributed roughly evenly between the sites) for the first patients enrolled to the phase 2 if they have both biopsiable disease and are randomized to SGI-110 + Irinotecan. Additional optional biopsy will be requested of patients with baseline research biopsy who remain on trial through Cycle 6-9.
 
i: QoL surveys will be done on C3D1 and every other cycle subsequently (i.e. Cycle 5 Day 1, Cycle 7 Day 1, etc)

**Arm B - Regorafenib**

	Pre-Study	C1 d1	C1 d8	C1 d15	C1 d22	C2 d1	C2 d8	C2 d15	C2 d22	C3 d1 a	C3 d8 a	C3 d15 a	C3 d22 a	Off Study b
Regorafenib c		X -----				X -----				X -----				
Informed consent	X													
History	X													
QoL questionnaire		X								X d				X
Concurrent meds	X	X		X		X		X		X				X
Physical exam (Ht, Wt, BSA, VS) e	X	X				X				X				X
Performance Status	X	X				X				X				X
Blood Pressure f		X	X	X	X	X	X							
CBC w/diff, plts	X	X		X		X		X		X				X
Serum chemistry g	X	X		X		X		X		X				X
Lipase		X												
CEA	X	X				X				X				X
Urinalysis	X													X
ECG	X													
Adverse event evaluation		X-----X												X
Tumor measurements	X	Repeated every 8 weeks. Documentation (radiologic) must be provided for subjects removed from study for progressive disease.												X b
Radiologic evaluation	X	Radiologic measurements should be performed every 8 weeks												X b
Archival Tissue	X													
B-HCG	X h													
Research Bloods		X		X		X		X		X				X

a: All study calendar evaluations for cycle 3 are representative of cycle 3 and beyond.  
b: Off-study evaluation should be performed within 30 days of last dose.  
c: Arm B (regorafenib 160 mg/day days 1-21). Treatment cycle is 28 days  
d: QoL surveys will be done on C3D1 and every other cycle subsequently (i.e. Cycle 5 Day 1, Cycle 7 Day 1, etc)  
e: Baseline height will be measured and recorded once pre-study, and this value for height will be used through the patient's duration of study  
f: Weekly blood pressures for first 6 weeks (can be checked with primary care physician or at patient's home), further blood pressure monitoring as determined by history of abnormality  
g: Albumin, alkaline phosphatase, total bilirubin, BUN, calcium, chloride, glucose, phosphorus, potassium, total protein, SGOT [AST], SGPT [ALT], sodium.  
h: Serum pregnancy test (women of childbearing potential).

CONFIDENTIAL

This document is confidential. Do not disclose or use except as authorized.

**Arm B – TAS-102**

	Pre-Stud	C1 d1	C1 d8	C1 d15	C1 d22	C2 d1	C2 d8	C2 d15	C2 d22	C3 d1 a	C3 d8 a	C3 d15 a	C3 d22 a	Off Study b
TAS-102 c		X-----				X-----				X-----				
Informed consent	X													
History	X													
QoL questionnaire		X								X d				X
Concurrent meds	X	X		X		X		X		X				X
Physical exam (Ht, Wt, BSA, VS) e	X	X				X				X				X
Performance Status	X	X				X				X				X
CBC w/diff, plts	X	X		X		X		X		X				X
Serum chemistry f	X	X		X		X		X		X				X
CEA	X	X				X				X				X
Urinalysis	X													X
ECG	X													
Adverse event evaluation		X-----X												X
Tumor measurements	X	Repeated every 8 weeks. Documentation (radiologic) must be provided for subjects removed from study for progressive disease.												X b
Radiologic evaluation	X	Radiologic measurements should be performed every 8 weeks												X b
Archival Tissue	X													
B-HCG	X g													
Research Bloods		X		X		X		X		X				X

a: All study calendar evaluations for cycle 3 are representative of cycle 3 and beyond.  
b: Off-study evaluation should be performed within 30 days of last dose.  
c: Arm B (TAS-102 35mg/m2 twice a day on Days 1-5 and 8-12). Treatment cycle is 28 days  
d: QoL surveys will be done on C3D1 and every other cycle subsequently (i.e. Cycle 5 Day 1, Cycle 7 Day 1, etc)  
e: Baseline height will be measured and recorded once pre-study, and this value for height will be used through the patient's duration of study  
f: Albumin, alkaline phosphatase, total bilirubin, BUN, calcium, chloride, glucose, phosphorus, potassium, total protein, SGOT [AST], SGPT [ALT], sodium.  
g: Serum pregnancy test (women of childbearing potential).

CONFIDENTIAL

This document is confidential. Do not disclose or use except as authorized.

## 10 MEASUREMENT OF EFFECT

As epigenetic agents may take many months to show their benefit as seen in MDS/AML studies, in both Phase 1 and Phase 2, subjects receiving SGI-110 + irinotecan may continue receiving their assigned treatment if their disease progresses based on RECIST 1.1 criteria if 1) the patient is clinically stable, 2) the patient is informed of their scan results and agrees to continue therapy, and 3) the patient's provider agrees that remaining on study would be appropriate for the patient.

Although response is not the primary endpoint of this trial, participants with measurable and/or non-measurable disease will be assessed by RECIST 1.1 criteria. For the purposes of this study, participants should be reevaluated approximately every 8 weeks. In addition to a baseline scan, confirmatory scans should also be obtained at least 4 weeks following initial documentation of an objective response.

### 10.1 Antitumor Effect– Solid Tumors

For the purposes of this study, participants should be re-evaluated for response every 8 weeks. In addition to a baseline scan, confirmatory scans should also be obtained not less than 4 weeks following initial documentation of objective response.

Response and progression will be evaluated in this study using the new international criteria proposed by the Response Evaluation Criteria in Solid Tumors (RECIST) 1.1 guideline. Changes in the diameter (unidimensional measurement) of the tumor lesions are used in the RECIST criteria.

#### 10.1.1 Definitions

Evaluable for toxicity. All participants who receive at least one dose of study treatment will be evaluable for toxicity from the time of their first treatment.

Evaluable for objective response. Only those participants who have measurable disease present at baseline, have received at least one cycle of therapy, and have had their disease re-evaluated will be considered evaluable for response. These participants will have their response classified according to the definitions stated below. (Note: Participants who exhibit objective disease progression or die prior to the end of cycle 1 will also be considered evaluable).

#### 10.1.2 Disease Parameters

Measurable disease. Measurable disease is the presence of at least one (1) lesion that can be accurately measured in at least one dimension with longest diameter  $\geq 20$  millimeters (mm) using conventional techniques (CT, MRI, x-ray) or  $\geq 10$  mm with spiral CT scan. Measurable lesions must be at

CONFIDENTIAL

This document is confidential. Do not disclose or use except as authorized.

least 2 times the slice thickness in mm. All tumor measurements must be recorded in millimeters (or decimal fractions of centimeters).

**Reminder:** A lesion in a previously irradiated area is not eligible for measurable disease unless there is objective evidence of progression of the lesion prior to study enrollment. Lesions in previously irradiated areas must be clearly identified as such.

Malignant lymph nodes. To be considered pathologically enlarged and measurable, a lymph node must be  $\geq 15$  mm in short axis when assessed by CT scan (CT scan slice thickness recommended to be no greater than 5 mm). At baseline and in follow-up, only the short axis will be measured and followed.

Non-measurable disease.

All other lesions (or sites of disease), including small lesions (longest diameter  $< 10$  mm or pathological lymph nodes with  $\geq 10$  to  $< 15$  mm short axis, are considered non-measurable disease. Bone lesions, leptomeningeal disease, ascites, pleural/pericardial effusions, lymphangitis cutis/pulmonis, inflammatory breast disease, abdominal masses identified by physical exam that are not measurable by reproducible imaging techniques, and cystic lesions are all considered non-measurable.

Target lesions.

All measurable lesions up to a maximum of 2 lesions per organ and 5 lesions in total, representative of all involved organs, should be identified as target lesions and recorded and measured at baseline. Lesions must be accurately measured in 1 dimension with a minimum size of 10 mm by CT or MRI (slice thickness no greater than 5 mm), 20 mm by *chest* x-ray. Nodes must have a short axis  $\geq 15$  mm. The short axis should be included in the sum of the lesions in the calculation of response. Nodes that shrink to  $< 10$  mm are considered normal. Target lesions should be selected on the basis of their size, be representative of all the involved organs, and should be lesions that can be followed with reproducible repeated measurements.

Lytic bone lesions or mixed lytic-blastic lesions, *with identifiable soft tissue components*, that can be evaluated by cross sectional imaging techniques such as CT or MRI can be considered target lesions if the *soft tissue component* meets the definition of measurability as defined above. Cystic lesions thought to represent cystic metastases can be considered as target lesions. However, if non-cystic lesions are present, these are preferred for selection as target lesions. Lesions in previously irradiated areas or areas subject to other loco-regional therapy are usually not considered measurable unless there has been demonstrated progression of that lesion.

CONFIDENTIAL

This document is confidential. Do not disclose or use except as authorized.

### Non-target lesions.

All other lesions, including small lesions < 10 mm or pathological lymph nodes measuring  $\geq$  10 mm to < 15 mm in short axis, as well as truly non-measurable lesions, which include leptomeningeal disease, ascites, pleural or pericardial effusion, inflammatory breast disease, lymphangitic involvement of skin or lung, abdominal masses identified by physical exam that are not measurable by reproducible imaging techniques.

#### 10.1.3 Methods for Evaluation of Measurable Disease

All measurements should be taken and recorded in metric notation, using a ruler, calipers, or digital measurement tool. All baseline evaluations should be performed as closely as possible to the beginning of treatment and never more than 4 weeks before the beginning of the treatment.

The same method of assessment and the same technique should be used to characterize each identified and reported lesion at baseline and during follow-up. Imaging-based evaluation is preferred to evaluation by clinical examination when both methods have been used to assess the anti-tumor effect of a treatment.

Clinical lesions. Clinical lesions will only be considered measurable when they are superficial (e.g., skin nodules and palpable lymph nodes). For the case of skin lesions, documentation by color photography, including a ruler to estimate the size of the lesion, is recommended.

Chest x-ray. Lesions on chest x-ray are acceptable as measurable lesions when they are clearly defined and surrounded by aerated lung; however, CT is preferable.

Conventional CT and MRI. These techniques should be performed with cuts of 10 mm or less in slice thickness contiguously. Spiral CT should be performed using a 5 mm contiguous reconstruction algorithm. This applies to tumors of the chest, abdomen, and pelvis. Head and neck tumors and those of extremities usually require specific protocols.

Ultrasound (US). When the primary endpoint of the study is objective response evaluation, US should not be used to measure tumor lesions. It is, however, a possible alternative to clinical measurements of superficial palpable lymph nodes, subcutaneous lesions, and thyroid nodules. US might also be useful to confirm the complete disappearance of superficial lesions usually assessed by clinical examination.

FDG PET and PET/CT. FDG PET will not be used for response assessment

CONFIDENTIAL

This document is confidential. Do not disclose or use except as authorized.

Endoscopy, Laparoscopy. The utilization of these techniques for objective tumor evaluation has not yet been fully and widely validated. Their uses in this specific context require sophisticated equipment and a high level of expertise that may only be available in some centers. Therefore, the utilization of such techniques for objective tumor response should be restricted to validation purposes in reference centers. However, such techniques may be useful to confirm complete pathological response when biopsies are obtained.

Tumor markers. Tumor markers alone cannot be used to assess response. If markers are initially above the upper normal limit, they must normalize for a subject to be considered in complete clinical response.

#### 10.1.4 Response Criteria

##### 10.1.4.1 Evaluation of Target Lesions

###### Complete Response (CR):

Disappearance of all target lesions. Any pathological lymph node must have reduction in short axis to < 10 mm.

###### Partial Response (PR):

At least a 30% decrease in the sum of the diameters of target lesions, taking as reference the baseline sum diameters.

###### Progressive Disease (PD):

At least a 20% increase in the sum of the diameters of target lesions, taking as reference the smallest sum on study with at least a 5 mm absolute increase in the sum of all lesions. The appearance of one or more new lesions\* denotes disease progression.

###### Stable Disease (SD):

Neither sufficient shrinkage to qualify for PR nor sufficient increase to qualify for PD, taking as reference the smallest sum diameters while on study.

Unknown (UN): Assessment of target lesions cannot be made due to insufficient or unevaluable data. In this case, a concise explanation must be given.

CONFIDENTIAL

This document is confidential. Do not disclose or use except as authorized.

**Note:** If tumor response data is missing for target lesions, the overall assessment must be UN unless there is new disease that would result in an overall assessment of PD. However, if there is missing or unevaluable data for non-target lesions, but data is available for all target lesions, the overall response for that time point will be assigned based on the sum LD of all target lesions. Additionally, the assessment of CR cannot be made if there is missing or unevaluable data for non-target lesions. In this case, the overall assessment would be PR.

**\*Definition of New Lesion:** The finding of a new lesion should be unequivocal (i.e. not due to difference in scanning technique, imaging modality, or findings thought to represent something other than tumor (ex: new bone lesions may be healing or flare of pre-existing lesions). However, a lesion identified on a follow-up scan in an anatomical location that was not scanned at baseline is considered new and will indicate PD. If a new lesion is equivocal (because of small size, etc.), follow-up evaluation will clarify if it truly represents new disease and if PD is confirmed, progression should be declared using the date of the initial scan on which the lesion was discovered.

#### 10.1.4.2 Evaluation of Non-Target Lesions

**Complete Response (CR):** Disappearance of all non-target lesions and normalization of tumor marker level. All lymph nodes must be non-pathological in size (< 10 mm short axis).

**Note:** If tumor markers are initially above the upper normal limit, they must normalize for a subject to be considered in complete clinical response.

**Incomplete Response/Stable Disease (SD):** Persistence of one or more non-target lesions and/or maintenance of tumor marker level above the normal limits.

**Progressive Disease (PD):** Appearance of one or more new lesions\* (new lesions must be > slice thickness) and/or unequivocal progression of existing non-target lesions.

Overall level of substantial worsening that merits discontinuation of therapy. A useful test that can be applied when assessing non-targets for unequivocal progression is to consider if the increase in overall disease burden based on the change in non-measurable disease is comparable in magnitude to the increase that would be required to declare PD for measurable disease.

CONFIDENTIAL

This document is confidential. Do not disclose or use except as authorized.

**Unknown (UN):** Assessment of non-target lesions cannot be made due to insufficient or unevaluable data. In this case, a concise explanation must be given.

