$\leq 1$ out of 6 at highest dose level below the maximally administered dose	This is generally the recommended phase 2 dose. At least 6 patients must be entered at the recommended phase 2 dose.

Toxicity will be evaluated using the NCI Common Terminology Criteria for Adverse Events Active Version. The frequency of toxicities per organ system will be tabulated using descriptive statistics. All patients who receive any amount of the study drug will be evaluable for toxicity.

### 5.1.3 Stage 2

The second stage of this study will be conducted as an open-label, randomized trial. As of December 2015, the maximally tolerated dose from the phase I trial was determined at level 1G:

- SGI-110 45mg/m^2 SC D 1-5
- Irinotecan 125mg/m^2 IV D 8 and 15

CONFIDENTIAL

This document is confidential. Do not disclose or use except as authorized.

- Mandatory growth factor support during cycle 1:
  - Filgrastim (or institutional equivalent) 5mcg/kg SC C1 D 9-14
  - Peg-filgrastim 6mg SC C1 D16
  - Additional growth factor support during Cycle 1 and subsequent cycles per clinician judgment

Ninety-six eligible subjects will be randomized in a 2:1 ratio to receive either (1) SGI-110+irinotecan combination treatment in 28-day cycles (n=64) or (2) regorafenib 160 mg QD days 1-21 in 28-day cycles or TAS-102 35mg/m^2 BID days 1-5 and 8-12 in 28-day cycles as per physician choice (n=32). Safety data will be reviewed at least on a quarterly basis by the SRC.

**As epigenetic agents may take many months to show their benefit as seen in MDS/AML studies, in both Stage 1 and Stage 2, subjects receiving SGI-110 + irinotecan may continue receiving their assigned treatment if their disease progresses based on RECIST criteria, version 1.1 if 1) the patient is clinically stable, 2) the patient is informed of their scan results and agrees to continue therapy, and 3) the patient provider agrees that remaining on study would be appropriate for the patient.**

Crossover to the SGI-110+irinotecan combination treatment arm of the study will be permitted for subjects in the regorafenib/TAS-102 arm after there is evidence of disease progression.

Response and PFS will be evaluated from images by the designated investigators at each site.

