## 5.6 Duration of Therapy

Duration of therapy will depend on individual response, evidence of disease progression and tolerance. In the absence of treatment delays due to adverse events, patients may continue on treatment until one of the following criteria applies:

- Disease progression (for regorafenib or TAS-102 arm in Phase II), see below \* regarding SGI-110 + irinotecan cohort.
- Intercurrent illness that prevents further administration of treatment,
- Unacceptable adverse event(s),

CONFIDENTIAL

This document is confidential. Do not disclose or use except as authorized.

- Participant demonstrates an inability or unwillingness to comply with the medication regimen and/or documentation requirements
- Participant decides to withdraw from the study, or
- General or specific changes in the participant's condition render the participant unacceptable for further treatment in the opinion of the treating investigator.

\*In both Stage 1 and Stage 2, subjects receiving SGI-110 + irinotecan may continue receiving their assigned treatment if their disease progresses based on RECIST criteria if 1) the patient is clinically stable, 2) the patient is informed of their scan results and agrees to continue therapy, and 3) the patient's provider agrees that remaining on study would be appropriate for the patient.

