**10.1.6 Progression-Free Survival**

Progression-Free Survival (PFS) is defined as the duration of time from start of treatment to time to progression event, including objective disease progression, clinical deterioration attributed to disease, or death.

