**Moving to Phase II Component:** Our hypothesis is that SGI-110 treatment will sensitize colon cancer patients to retreatment with irinotecan. Accordingly, it will be important to see that the dose of SGI-110 that is at the MTD does have pharmacodynamics effects at the tumor level. Patient tumor biopsies post-treatment will be analyzed by LINE assay for demethylation to assess for at least 10% demethylation from baseline in the tumor biopsies. We aim to see this level of demethylation in at least 60% of post-treatment biopsies as previously described in phase O studies.

**Phase II primary objective:** Evaluate the progression free survival (PFS) in patients receiving combination SGI-110 plus Irinotecan compared to standard of care treatment with regorafenib or TAS-102. Events are defined as disease progression or death from any cause. All patients treated

CONFIDENTIAL

This document is confidential. Do not disclose or use except as authorized.

on protocol will be included in the determination of PFS, regardless of treatment modification or discontinuation.

Epigenetic therapy may take several cycles to exert its maximal benefit, and preclinical data has demonstrated initial tumor growth is possible prior to tumor shrinkage. Patients on treatment with SGI-110 and IRI will be allowed to remain on study if their tumor progresses on RECIST 1.1 criteria if they are 1) clinically stable, 2) their provider feels it would be in their best interest, and 3) the patient is informed of scan results and consents to remain on treatment. In this circumstance, they will be reimaged on schedule after 2 further cycles. If this subsequent imaging confirms progressive disease, the date of the progression even will be dated to the first (initial) scan date that progression was first documented.

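### Non-target progression is described partly by a treatment judgement while only Arm A may be treated past progression and has a confirmation step, so unblinded readers could record PFS events unevenly

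*Combined protocol and SAP*

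**What the plan says.** **Non-target progression.** Section 10.1.4.2 requires new lesions and/or unequivocal progression of existing non-target lesions. It then adds a free-standing phrase: "Overall level of substantial worsening that merits discontinuation of therapy". The next sentence asks whether the increase in overall burden is "comparable in magnitude to the increase that would be required to declare PD for measurable disease", but presents this as a useful test that may be applied, not as a requirement. A footnote to the best-response table in Section 10.1.4.3 says that non-target progression may be accepted as progression in exceptional circumstances.

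**Treatment after progression.** Section 5.1.3 says that SGI-110 + irinotecan patients "may continue receiving their assigned treatment if their disease progresses based on RECIST criteria, version 1.1", given clinical stability, the patient's informed agreement and the provider's view that staying on study is appropriate. Sections 5.6, 10 and 14.1 repeat this in substance. For control, Section 5.6 lists as a reason to stop: "Disease progression (for regorafenib or TAS-102 arm in Phase II". Sections 5.1.3 and 5.8 then open crossover to Arm A.

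**The PFS event.** Section 14.1 (Phase II primary objective) states: "Events are defined as disease progression or death from any cause". It counts all treated patients whatever happens to their treatment. Arm A patients who continue are re-imaged after two further cycles: "If this subsequent imaging confirms progressive disease, the date of the progression even will be dated to the first (initial) scan date" on which progression was first documented. Section 10.1.6 words the event differently, "including objective disease progression, clinical deterioration attributed to disease, or death".

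**Who reads the scans.** Designated investigators at each site evaluate PFS (Section 5.1.3). Treatment is not blinded (Section 4.3).

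**The concern.** A progression criterion should describe the tumour. Here part of the description of non-target progression asks whether therapy ought to stop, and the rules on stopping differ by arm. For non-target-only growth in Arm A, an investigator who decides that continuing is appropriate may feel that the worsening does not merit discontinuation and leave progression unrecorded at that scan. In Arm B nothing pulls that way: progression ends treatment and gives access to the experimental combination.

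If this happened, some Arm A events would be recorded at least one scan late and control events would not. That favours Arm A on the primary endpoint without any drug effect. The re-imaging step in Section 14.1 adds a second possible asymmetry, for every type of progression, because Arm A alone gets a second look.

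**Working it through.** **Step 1: what the text settles.**
- Target-lesion progression is numerical (Section 10.1.4.1), and a new lesion is progression in its own right. The discontinuation phrase matters only when existing non-target lesions are the sole evidence. All patients need measurable disease (3.1.5). However, targets are capped at 2 per organ and 5 in total (10.1.2), so further lesions, ascites and effusions fall in the non-target group.
- If progression is recorded on the first scan and confirmed on the next, Section 14.1 dates it to the first. No delay arises.
- If progression is not recorded on the first scan, there is no earlier documentation to date back to. The event moves by at least one scan.
- If progression is recorded and the next scan does not confirm it, Section 14.1 does not say whether the first reading is an event. No matching re-imaging rule exists for control.

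**Step 2: size of one delay.** Scans are every 8 weeks (Section 10): 56 / 30.44 = 1.84 months, against an assumed control median of 1.9 months (Section 14.1).

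**Step 3: effect on the test (illustration).** Inputs from Section 14.1: 64 versus 32 patients, one-sided 0.05 log-rank test, 2 years of accrual plus 2 years of follow-up. Hazard ratio set to 1, event times rounded up to the next 8-week scan, no dropout. A share f of Arm A events is recorded 8 weeks late. The documents do not give f; it is assumed.

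Two control curves were used: exponential with median 1.9 months (1.9 × 4.345 = 8.26 weeks), and the plan's printed piecewise hazards. These differ. The printed rates give a cumulative hazard at week 12 of 6 × 0.0113 + 6 × 0.0558 = 0.4026, so the median is 12 + (0.6931 − 0.4026) / 0.3238 = 12.9 weeks. Both are shown as a range.

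The plan's own null scenario rejects in 5.4% of the studies not stopped for futility, and in 4.0% overall. With f = 0 and no futility stop, the simulation gives 5.1% (exponential) and 5.3% (piecewise), so the starting point agrees.

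| f | Arm A patients (f × 64) | One-sided type I error |
|---|---|---|
| 0 | 0 | 5.1–5.3% |
| 1–2.5% | 0.6–1.6 | 5.6–6.3% (exponential) |
| 5% | 3.2 | 7.4% (exponential) to 9.2% (piecewise) |
| 10% | 6.4 | 10.4% (exponential) to 14.2% (piecewise) |

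The 1–2.5% row used 10,000 runs and its own zero-delay baseline was 5.5%; the other rows used 5,000. Simulation standard error is about √(0.05 × 0.95 / 5,000) = 0.3 points. A repeat of 10,000 runs with another seed gave 6.2% and 6.6% (exponential) and 6.1% and 7.1% (piecewise) for f = 1% and 2.5%, so the decimals should not be leaned on.

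**Step 4: where f might lie.** If 2–5% of progressions are non-target-only and half of those in Arm A are deferred once, f = 1–2.5%. If the share is 10–20%, f = 5–10%. Neither share has a source in the documents.

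**The case against.** The strongest reply is about sequence. Section 10 lets Arm A patients continue when they "may continue receiving their assigned treatment if their disease progresses based on RECIST 1.1 criteria", so progression is declared first and the treatment decision follows. If choosing to continue cancelled the progression, the continuation rule would have nothing to act on. The disputed phrase speaks of a level of worsening, not of whether therapy is actually stopped, and it names no arm. The stated criterion is unequivocal progression, and an arm-neutral size comparison follows directly. Section 14.1 counts events regardless of treatment changes and back-dates confirmed progression. Non-target-only progression is treated as exceptional.

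Most of this stands. A reader might infer that the plan makes the same non-target growth an event in control and a non-event in Arm A, or that the false-positive rate is thereby known to be inflated. The documents support neither reading: no sentence ties progression to arm, and no figure gives the share of events affected.

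Three things remain. For existing non-target lesions, the description of progression itself contains a treatment judgement, so the order of declaring and deciding is not clean. The size comparison that would remove the ambiguity is optional. Back-dating needs a first scan that was called progression, and the rule for an unconfirmed call is missing. Some of this risk is ordinary open-label reading, but the wording gives it a foothold that can be removed.

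**Conclusion.** The point holds as an ambiguity in the primary endpoint that could act in one direction, not as an arm-dependent rule. It has two parts: the discontinuation phrase in Section 10.1.4.2, which is narrow in scope, and the Arm-A-only re-imaging step in Section 14.1, which applies to all types of progression and leaves an unconfirmed first call undefined.

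The size is not known. At the low assumed shares (1–2.5% of Arm A events, about one or two patients) the effect on type I error is around one percentage point, little more than simulation noise. At 5–10% (about three to six patients) the error would rise to roughly 7–14%. These figures rest on the assumed share, a single 8-week delay, no delay in control, and no futility stop. The direction does not depend on the share: delay confined to Arm A favours Arm A. This is a cheap improvement to make, not evidence that the comparison is invalid.

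**What to change.** Change endpoint wording only, and leave the treatment-continuation rules as they are:

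1. In Section 10.1.4.2, remove the discontinuation phrase as a criterion, and make the tumour-burden comparison the rule for unequivocal non-target progression in both arms.
2. State that the PFS event is the first RECIST 1.1 progression in both arms, and that a decision to continue treatment has no bearing on whether, or on what date, progression is recorded.
3. Reconcile Sections 10.1.4.2, 10.1.4.3 (footnote), 10.1.6 and 14.1 so that one confirmation and dating rule applies to both arms. The rule should say how an unconfirmed first progression counts and whether clinical deterioration is an event.

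The cost is a short amendment to the text. The one downside is that some Arm A events may be recorded earlier, so Arm A PFS may look slightly shorter.
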